Revised the definition of the study population	Broadened the inclusion criteria for the trial. In addition to enrolling patients with TG value >880 mg/dL at the screening visit, also allowing patients with a TG value at screening >500 mg/dL if they have a prior fasting measurement >1000 mg/dL or if they have had 2 or more episodes of pancreatitis in the past 24 months.	Clinical Study Synopsis, Target Population, Statistical Plan Section 3.2.1 Rationale for Study Design Section 2.1 Primary Objective Section 6.1 Study Description and Duration Figure 1 Study Flow Diagram Section 7.2.1 Inclusion Criteria, #3
Broadened the entry criteria with regard to fasting TG values at study entry and consequently removed Visit 2 during the Screening Period; Extended the time period for patients having a documented history of HTG from 15 to 24 months of screening	See rationale above. Since requiring only a single TG screening value, eliminating visit 2 which had the purpose of checking a second screening value. This decreases the burden on participants and sites, while still enrolling patients who have demonstrated high fasting TG values.	Clinical Study Protocol Synopsis, Objectives, Study Design, Study Duration Section 2.1 Primary Objective Section 3.1 Hypotheses Section 3.2.1 Rationale for Study Design Section 6.1 Study Description and Duration Section 7.2.1 Inclusion Criteria, Criterion #2 Table 1 Schedule of Events for DBTP Section 11.4.3.1 Primary Efficacy Analysis
Broadened the entry criteria with regard to BMI at study entry	Feedback from investigators and experts in this area have stated that a BMI range of 18-40 is too restrictive. Therefore the upper limit was increased to 45.	Section 7.2.1 Inclusion Criteria, Criterion #5
Added exclusion criterion for patients with a history of hypersensitivity to study drug or excipients, and for patients having received COVID-19 vaccination within 1 week of start of study medication.	The exclusion for hypersensitivity was an omission in the last version of the protocol that is now being updated. The exclusion for COVID-19 was added as the study drug has not been tested together with vaccines for COVID-19.	Section 7.2.2 Exclusion Criteria, new criteria #20, and #21 Section 8.9.1 Prohibited Medications

Reduced the off-drug follow-up period from 48 weeks to 20 weeks and the total study duration from 100 weeks to 72 weeks	Feedback from investigators, experts, and potential patients has been that a 48-week off-drug follow-up period is excessive and discourages participation. Other studies have demonstrated that evinacumab serum concentrations are minimal (ie, <1 ug/mL and <1% of C _{max}) by 24 weeks after the last drug administration	Clinical Study Protocol Synopsis, Study Design, Study Duration Section 3.2.1 Rationale for Study Design Section 6.1 Study Description and Duration Figure 1 Study Flow Diagram Section 8.3.2 Study Drug Discontinuation Table 1 Schedule of Events for the DBTP Table 2 Schedule of Events for the Off-Drug Follow-up Period
Revised definition of study follow-up period	Patient disposition summaries were adjusted to align with the 20-week follow-up period. Simplified the definition of screened patients. Simplified the descriptions of TEAE summaries that will be provided.	Section 11.4.1 Patient Disposition Section 11.4.5.1 Adverse Events
Distinguished separate timepoints for collection of lipids and special lipids	This was an oversight in the last version of the protocol. Special Lipids (ApoC3, ApoB48, ApoB100, and ApoB Total) collections were reduced as was the original intention.	Table 1 Schedule of Events for the DBTP Table 2 Schedule of Events for the Off-Drug Follow-up Period Section 9.1.1.1 Footnotes for Table 1 Schedule of Events (DBTP), #6 Section 9.1.1.2 Footnotes for Table 2 Schedule of Events (Off Drug Follow-up Period), #1 Section 9.2.2.2 Fasting Blood Samples for Assessment of Lipid Profile (For Efficacy and PD Variables)
Specified that immunogenicity sample collection should occur prior to infusion	This corrects an error in the prior version. Immunogenicity only needs to be sampled prior to infusion.	Section 9.1.1.2 Footnotes for Table 2 Schedule of Events (Off Drug Follow-up Period), #6
Removed eligibility criteria redundant text	To minimize repetition of identical text to avoid discrepancies and enhance readability	Clinical Study Protocol Synopsis, Study Design
Added APOE genotypes to the list of genes encoding proteins in the LPL pathway	APOE genotypes will be explored when patients are sequenced to assess their response to evinacumab	Section 1 Introduction
Revised screening language to allow the potential for patients who failed screening to be rescreened following a discussion with the medical monitor	To enhance enrollment	Section 6.1 Study Description and Duration
Editorial change related to genotypic or other biomarker differences	Revised for clarity	Section 2.3 Exploratory Objectives

Amendment 1

The following table outlines the changes made to the protocol and the affected sections:

Description of Change	Brief Rationale	Section # and Name
The schedule of events were updated to add “weight” at each dosing visit and during in-person visits in the off-drug follow up period. Correspondingly, weight was added as an assessment in the Safety Procedures section.	Body weight measurement is needed for treatment dosing which is weight-based, and for safety assessment. Weight was inadvertently omitted in the original protocol.	Table 1. Schedule of Events for the DBTP Table 2. Schedule of Events for the Off-Drug Follow-Up Period Section 9.2.3.1 Vital Signs and Body Weight

LIST OF ABBREVIATIONS AND DEFINITIONS OF TERMS

ADA	Anti-drug antibody
AE	Adverse event
AESI	Adverse event of special interest
ALT	Alanine aminotransferase
ANGPTL3	Angiopoietin-like 3
APAC	Acute Pancreatitis Adjudication Committee
APO	Apolipoprotein
AP	Acute pancreatitis
AST	Aspartate aminotransferase
β-HCG	Human chorionic gonadotrophin
BMI	Body mass index
BUN	Blood urea nitrogen
CABG	Coronary artery bypass grafting
CI	Confidence interval
COA	Clinical outcome assessment
CPK	Creatine phosphokinase
CRF	Case report form (electronic or paper)
CRO	Contract research organization
CT	Computer tomography
DBTP	Double-blind treatment period
DNA	Deoxyribonucleic acid
EC	Ethics committee
ECG	Electrocardiogram
EDC	Electronic data capture
eCRF	Electronic case report form
eGFR	Estimated glomerular filtration rate
FBR	Future biomedical research
FCS	Familial chylomicronemia syndrome
FH	Familial hypercholesterolemia
FSH	Follicle-stimulating hormone
FT4	Free thyroxine
GCP	Good Clinical Practice
HbA1c	Glycosylated hemoglobin
HDL	High-density lipoprotein
HDL-C	High-density lipoprotein cholesterol
HoFH	Homozygous familial hypercholesterolemia

HTG	Hypertriglyceridemia
ICF	Informed consent form
ICH	International Council for Harmonisation
IDMC	Independent Data Monitoring Committee
IEC	Independent ethics committee
IRB	Institutional review board
ITT	Intent to treat
IV	Intravenous
IVRS	Interactive voice response system
IWRS	Interactive web response system

13.5.	Clinical Study Data Transparency	77
14.	PROTOCOL AMENDMENTS	78
15.	PREMATURE TERMINATION OF THE STUDY OR CLOSE-OUT OF A SITE	79
15.1.	Premature Termination of the Study.....	79
15.2.	Close-out of a Site	79

16.	CONFIDENTIALITY	79
17.	FINANCING AND INSURANCE.....	79
18.	PUBLICATION POLICY	79
19.	REFERENCES	80
20.	INVESTIGATOR'S AGREEMENT.....	81
	SIGNATURE OF SPONSOR'S RESPONSIBLE OFFICERS	82

LIST OF TABLES

Table 1:	Schedule of Events for the DBTP.....	46
Table 2:	Schedule of Events for the Off-Drug Follow-up Period.....	48

LIST OF FIGURES

Figure 1:	Study Flow Diagram	30
-----------	--------------------------	----

CLINICAL STUDY PROTOCOL SYNOPSIS

Title	A Randomized, Double-Blind, Placebo-Controlled Study to Evaluate the Efficacy and Safety of Evinacumab in Patients with Severe Hypertriglyceridemia for the Prevention of Recurrent Acute Pancreatitis
Site Locations	Multiple centers in North America and the European Union (EU)
Principal Investigator	A coordinating principal investigator will be identified prior to the start of the study
Objectives	
The primary objective of the study is to determine the proportion of patients with elevated triglycerides (TG), without Familial Chylomicronemia Syndrome (FCS) due to loss of function (LoF) mutations in lipoprotein lipase (LPL), and a history of hypertriglyceridemia (HTG)-associated acute pancreatitis (AP) who experience a recurrent episode of AP after treatment with evinacumab versus placebo.
 
The secondary objectives of the study are:
 
• To determine the change in the standard lipid profile after therapy with evinacumab versus placebo• To determine the changes in specialty lipoprotein parameters (ApoC3, ApoB48, ApoB100, and nuclear magnetic resonance [NMR] lipid profile) after therapy with evinacumab versus placebo• To measure the number of AP episodes per patient• To assess the safety and tolerability of evinacumab• To assess the potential immunogenicity of evinacumab• To assess the concentrations of total evinacumab and total angiopoietin-like 3 (ANGPTL3)
Study Design	
This is a phase 2b, multicenter, international, randomized, placebo-controlled study intended to demonstrate that evinacumab can prevent recurrent AP episodes in patients with severe hypertriglyceridemia (sHTG) and a recent history of HTG-associated AP. Approximately 120 adult patients will be randomized 1:1 to receive evinacumab or matching placebo.
 
The study consists of 3 periods: a screening period, a double-blind treatment period (DBTP), and a safety follow-up period. The screening period of up to 28 days will determine participant eligibility and will include an evaluation of prior episodes of HTG-associated AP, genotyping to exclude patients with familial chylomicronemia syndrome (FCS) due to loss of

function mutations in lipoprotein lipase (LPL), and a measurement of fasting TG levels.

Patients who fulfill all the eligibility criteria will be randomized and receive their first dose of assigned study drug on day 1, with subsequent doses administered approximately every 4 weeks (Q4W) during the 52-week DBTP. This will be followed by a 20-week off-drug follow-up period.

Efficacy will be assessed by measuring the number of patients with at least 1 independently adjudicated positive event of AP over 52 weeks of treatment with evinacumab versus placebo. The study will have an independent committee to adjudicate these episodes in accordance with clinical standards for diagnosis of AP. Efficacy will also be assessed by clinical laboratory evaluation of lipid levels at pre-specified time points throughout the study.

Safety will be assessed throughout the study by comparing the frequency and severity of adverse events (AEs) between the evinacumab and placebo groups, as well as evaluating abnormal laboratory findings, electrocardiogram (ECG) findings, and anti-drug antibody (ADA) and neutralizing antibodies (NAb) assessments.

Study Duration

The duration of the treatment period for individual patients is 52 weeks, after which patients will continue in a 20-week follow-up period for a total study duration of 72 weeks, excluding the screening period.

End of Study Definition

The end of study is defined as the date the last patient completes the last study visit, withdraws from the study, or is lost to follow-up (ie, the patient can no longer be contacted by the investigator).

Population

Sample Size: Approximately 120 patients

Target Population: Adult patients 18 to 80 years of age without FCS due to LPL loss of function mutations with elevated baseline fasting TGs and AP criteria as follows:

- Fasting serum TG values >880 mg/dL (10 mmol/L) determined during the screening period and a documented history of 1 HTG-associated AP episode within 24 months of screening, or
- Fasting serum TG values >500 mg/dL (5.6 mmol/L) determined during the screening period in patients with a history of 2 or more HTG-associated AP episodes within 24 months of screening, or
- Fasting serum TG values >500 mg/dL (5.6 mmol/L) determined during the screening period and a documented fasted TG values >1000 mg/dL (11.3 mmol/L) and a history of

1 or more HTG-associated AP episodes(s) within 24 months of screening.

Treatment

Study Drug	Evinacumab
Dose/Route/Schedule:	20 mg/kg administered intravenously (IV) over a 1-hour infusion Q4W, ± 4 days
Placebo	Matching placebo
Route/Schedule:	Intravenous infusion Q4W (± 4 days)

Endpoints

Primary Efficacy: The primary endpoint is for efficacy: the proportion of patients with at least 1 positively adjudicated AP episode during the 52 weeks of the DBTP.

Secondary Efficacy:**Key Secondary Efficacy:**

- Percent change in ApoC3 from baseline to week 52
- Percent change in fasting TGs from baseline to week 52

Other Secondary Efficacy:

- Percent change in other fasting standard lipid profile parameters (total cholesterol [TC], non-high-density lipoprotein cholesterol [non-HDL-C]) from baseline to week 52
- Percent change in other fasting specialty lipoprotein parameters (ApoB48, ApoB100 levels, and NMR-determined particle size and number) from baseline to week 52
- Number of independently adjudicated episodes of AP per patient during 52 weeks of the DBTP

Safety Endpoints:

- Incidence and severity of treatment-emergent adverse event (TEAEs), serious adverse events (SAEs), laboratory abnormalities, and other safety variables in patients treated with evinacumab throughout the study

- Incidence of treatment-emergent ADA and NAb

Other Endpoints:

- The percent change in fasting HDL-C and LDL-C from baseline to week 52
- Concentrations of total evinacumab and total ANGPTL3 over time

Procedures and Assessments

Efficacy will be assessed by measurement of adjudicated events of AP, and measurement of lipids, specialty lipids, and lipoproteins.

Safety will be monitored via AE reporting, physical examinations, routine vital signs, clinical laboratory tests (blood chemistry and hematology), and standard 12-lead ECG.

Serum samples for the determination of total evinacumab and total ANGPTL3 concentrations, and ADA and NAb will be collected.

Serum and plasma samples will be collected for analysis of additional biomarkers.

Statistical Plan

The primary efficacy comparison will evaluate the evinacumab 20 mg/kg IV treatment group versus placebo, using the primary efficacy endpoint of the proportion of patients with at least 1 positively adjudicated AP event during the 52 weeks of DBTP (intent-to-treat [ITT] estimand-binary). The primary efficacy endpoint will be analyzed in the ITT population using the method of logistic regression, and the model will include at least treatment group, and number of historical AP episodes within the previous 24 months. The evinacumab group will be compared to the placebo group with odds ratio and 95% confidence interval (CI) provided for each treatment group. The statistical testing of the treatment group comparison for the primary measure will be evaluated at a 2-sided significance level of 0.049.

For early termination (ET) patients who did not complete the week 52 efficacy assessment, the missing primary endpoint will follow a data imputation strategy.

For the key secondary efficacy endpoints and other secondary efficacy endpoints collected in the DBTP, descriptive summaries and analyses will be performed in the ITT population, using values obtained regardless of adherence to study treatment and subsequent therapies (ITT estimands).

Safety results will be summarized descriptively by the treatment group.

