The primary endpoint was predefined as the mean within-patient change in TGs, and the study did not meet the threshold of a clinically important reduction (>40%). This applied to the overall study population and also for genotypic strata based on the presence of LPL pathway LoF mutations. Several factors may have contributed to a lack of efficacy. There was large variability in TGs, which was compounded by the absence of a diet-stabilization period and efficacy determined by a single post-treatment TG measurement. In addition, there was variability in drug exposure, where patients with the lowest trough levels of evinacumab had little to no treatment response. In this context, when examining median percent changes to minimize the impact of outliers, the evinacumab-treated patients overall showed a clinically important reduction (>40%) in fasting TGs at each post-baseline visit, culminating in a median reduction of approximately 57% at week 12 during the DBTP. The treatment effect was even more pronounced when excluding patients with FCS, where non-FCS patients had a median reduction in TGs of approximately 80%. When including patients that switched to evinacumab during the SBTP, the median percent reduction in TGs after 12 weeks of evinacumab exposure was approximately 70% for non-FCS patients.

In the DBTP, 5 patients (3 in the evinacumab group; 2 in the placebo group) experienced an episode of AP (all serious adverse events or SAEs); all resolved within 7 days. For the evinacumab-treated patients, 1 participant had FCS and did not have a TG response to therapy; 1 patient had an episode of AP within 48 hours after receiving his first dose of evinacumab; 1 patient had persistently low trough concentrations of evinacumab. Treatment-emergent adverse events (TEAEs) that occurred more frequently in the evinacumab group compared to the placebo group included Abdominal pain (14.3% versus 12.5%), Headache (11.4% versus 6.3%), and Constipation (8.6% versus 0). In the SBTP, 12 (25.5%) patients had SAEs of Acute pancreatitis; none was considered related to the study drug. The majority of episodes occurred during the off-drug period (>4 weeks after the last dose of evinacumab) and episodes of AP were not independently adjudicated, with some patients diagnosed with AP despite the absence of pathologic findings on pancreatic imaging and/or elevated lipase/amylase levels.

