4. ENDPOINTS

4.1. Primary Efficacy Endpoint

The primary efficacy endpoint is the proportion of patients with at least 1 positively adjudicated AP episode during the 52 weeks of the DBTP (intent-to-treat [ITT] estimand - binary).

The ITT estimand – binary used for the primary efficacy analysis is defined as the treatment policy strategy, specifically the occurrence of intercurrent events (ie adherence to study treatment and subsequent therapies) is irrelevant; the value for the primary efficacy endpoint is used regardless of whether or not intercurrent events occur (Section 11.4.3.1).

Note: AP is defined in Section 5.2.1.

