11.2. Justification of Sample Size

For the primary efficacy hypothesis during the DBTP, a total sample size of 120 patients (60 patients in each treatment group) will have 90% power to detect a treatment group difference in positively adjudicated AP event rates of 24% (placebo event rate: 30%; evinacumab event rate: 6%), with 0.049 two-sided significance level (data on file). This sample size has been adjusted for a 5% non-evaluable patient rate for the primary efficacy endpoint.

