11.4.5.1. Adverse Events

All AEs reported in this study will be coded using the currently available version of the Medical Dictionary for Regulatory Activities (MedDRA®). The verbatim text, the preferred term (PT), and the system organ class (SOC) will be provided in patient listings.

Definitions

For safety variables, the following observation periods are defined:

- The pre-treatment period is defined from the day the ICF is signed to the day before the first dose of double-blind study treatment.
- The TEAE observation period is defined from the day of the first dose of double-blind study treatment to the day of the last dose of double-blind study treatment + 168 days (24 weeks) (residual effect of treatment for IV dose regimen is expected until 24 weeks after the last dose of study drug).

The post-treatment observation period is defined as the time from the day after the end of the TEAE period to the last study visit.

Treatment-emergent adverse events are defined as those adverse events that developed, worsened, or became serious during the TEAE period.

Analysis

Adverse event incidence tables will present data by SOC sorted alphabetically and PT sorted by decreasing frequency, and summarize the number (n) and percentage (%) of patients experiencing an AE. Multiple occurrences of the same event in the same patient will be counted only once in the tables. Data conventions for missing or partial AE dates will be addressed in the SAP. The denominator for computation of percentages is the SAF population within each treatment group.

Summaries of TEAE incidences will include:

- All TEAEs
- All treatment-emergent SAEs, including patient deaths
- All treatment-emergent AESIs
- TEAEs by severity (according to the grading scale outlined in Section 10.2.5), depicting the worse TEAE severity for those patients with multiple occurrences of the same event
- All TEAEs leading to permanent treatment discontinuation

An AE patient listing will be provided for all patient deaths occurring during the TEAE period and the post-treatment period.

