#### ***Analysis of all treatment-emergent adverse events***

The following TEAE summaries will be generated:

- Overview of TEAEs, summarizing number (%) of patients with any
  - TEAE;
  - Serious TEAE;
  - TEAE leading to death;
  - TEAE leading to permanent treatment discontinuation.
- All TEAEs by primary SOC, HLGT, HLT, and PT
- All TEAEs by primary SOC and PT
- Number (%) of patients experiencing common TEAE(s) presented by primary SOC and PT (PT incidence  $\geq 5\%$  in any treatment group)
- All TEAEs relationship (related/not related) to evinacumab

- All TEAEs by maximum severity (i.e., mild, moderate or severe)

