***Analysis of all treatment emergent serious adverse event(s)***

- All Serious TEAEs by primary SOC, HLT, HLT, and PT
- All Serious TEAEs by primary SOC and PT
- Patient listings of serious TEAEs will be provided in the report appendix.
- All Serious TEAEs relationship (related/not related) to study treatment

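### No planned adverse-event total is shown without acute pancreatitis, so the drug's intended effect can offset an excess of other serious events in those totals

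*Protocol*

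**What the plan says.** The protocol synopsis, under Study Design, sets the comparison: "Safety will be assessed throughout the study by comparing the frequency and severity of adverse events (AEs) between the evinacumab and placebo groups". The sentence is repeated in protocol 6.1 and SAP 2.3. The summaries that carry it out are these:

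- Protocol 11.4.5.1 lists all TEAEs, "All treatment-emergent SAEs, including patient deaths", AESIs, TEAEs by severity and TEAEs leading to discontinuation.
- SAP 5.8.1 plans an "Overview of TEAEs, summarizing number (%) of patients with any" TEAE, serious TEAE, TEAE leading to death, or TEAE leading to permanent discontinuation. It adds "All Serious TEAEs by primary SOC and PT", a maximum-severity table and relatedness tables.
- SAP 5.8.1 also has a block on AP: suspected AP, positively adjudicated AP, AP by adjudication outcome, and a listing. That block treats AP events as TEAEs. They are tabulated in addition to the totals and not taken out of them.

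The primary endpoint in protocol 4.1 is "the proportion of patients with at least 1 positively adjudicated AP episode during the 52 weeks of the DBTP". Protocol 10.1.1 has the investigator record all clinical events and makes no exception for endpoint events. Protocol 11.4.5 and SAP 5.8 make all safety analysis descriptive.

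**The concern.** One event sits on both sides of the benefit-risk account. If evinacumab works as designed, it removes many AP episodes, and each one removed also lowers the any-TEAE and any-serious-TEAE counts in the evinacumab arm. AP will often be serious. The protocol introduction says that episodes frequently lead to hospital admission, and protocol 10.2.2 makes any admission a serious event. In the earlier phase 2 study all five patients with AP in the double-blind period had it recorded as an SAE, and "In the SBTP, 12 (25.5%) patients had SAEs of Acute pancreatitis" in the period that followed.

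The totals are therefore expected to favour evinacumab for a reason unrelated to its other harms. What is at stake is whether a reader of the overview could see a real excess of other serious events, particularly one spread thinly over many preferred terms.

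**Working it through.** **Inputs.** From protocol 11.2 and SAP 2.2: 60 patients per arm, 5% non-evaluable, "placebo event rate: 30%; evinacumab event rate: 6" (both in per cent), "with 0.049 two-sided significance level", and 90% power. Assumed, because the documents do not give it: a placebo rate of serious events other than AP of 5% to 15%.

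**The plan's own figure.** Evaluable patients are 60 × 0.95 = 57 per arm. The exact power of a two-sided Fisher test at 0.049 for 30% against 6% is 90.5%, so the stated 90% reproduces. The two rates are a fair basis for what follows. They correspond to 60 × 0.30 = 18 placebo and 60 × 0.06 = 3.6 evinacumab patients with AP.

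**Any-serious-event total.** Let A be the AP rate and q the rate of other serious events. If all AP is serious and independent of the rest, the total is 1 − (1 − A)(1 − q).

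- Other serious events doubled, 10% to 20%: placebo 1 − 0.70 × 0.90 = 37.0%; evinacumab 1 − 0.94 × 0.80 = 24.8%.
- Tripled, 10% to 30%: placebo 37.0%; evinacumab 1 − 0.94 × 0.70 = 34.2%.

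Rows without AP would show 10% against 20%, and 10% against 30%.

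**Break-even.** The totals are equal when the evinacumab rate of other serious events is 1 − 0.70(1 − q)/0.94, where q is the placebo rate. If only 80% of AP is serious, A becomes 24% and 4.8%, and the expression is 1 − 0.76(1 − q)/0.952.

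| Placebo, other serious events | Evinacumab rate for equal totals, all AP serious | Hidden excess | Same, 80% of AP serious | Hidden excess |
|---|---|---|---|---|
| 5% | 29.3% | 24.3 points | 24.2% | 19.2 points |
| 10% | 33.0% | 23.0 points | 28.2% | 18.2 points |
| 15% | 36.7% | 21.7 points | 32.1% | 17.1 points |

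**Dependence.** In the doubling example the reversal does not need independence when all AP is serious. The placebo total cannot be below 30% (complete overlap), and the evinacumab total cannot exceed 6% + 20% = 26% (no overlap). With 80% of AP serious, the corresponding limits are 24% and 4.8% + 20% = 24.8%. The direction is then no longer guaranteed at the extremes.

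**Time window.** The design rates cover 52 weeks, whereas TEAEs run to last dose + 168 days. With a last dose on day 337 (week 48), that is day 337 + 168 = 505, the end-of-study visit. The totals therefore also take in off-drug AP. If AP recurs in the evinacumab arm after dosing stops, the gap in A narrows and so does the masking.

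**The case against.** The best reply is that other planned outputs already separate AP from the rest.

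- SAP 5.8.1 gives TEAEs and serious TEAEs by relatedness. Under protocol 10.2.6 an event reasonably explained by the disease is not related, and the protocol introduction reports that none of the AP SAEs in the earlier study's single-blind period was judged related. The related-event rows should hold little AP.
- AP has its own preferred-term rows and tables, and AESIs are shown separately.
- The listings of serious TEAEs and of positively adjudicated AP let a reader count patients with another serious event.
- The SAP is an abbreviated, descriptive plan, written after the study stopped with few patients. Such listings can be read line by line.

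All of this stands, and it limits the point. A reader might infer that every planned safety summary is distorted, or that the count without AP cannot be recovered. The documents do not support either reading, given the relatedness tables and the listings. Nor do they support extending the point to discontinuations, because AP is not among the reasons for permanent discontinuation in protocol 8.3.2.1.

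What the reply does not supply is the count itself. Relatedness rests on investigator judgement. Term rows cannot be subtracted, because one patient may have both AP and another serious event. A hand count from listings is not a planned between-arm result.

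**Conclusion.** The point holds for the patient-level totals of any TEAE, any serious TEAE and maximum severity. At the design rates they tilt toward evinacumab. With all AP serious and independent of other serious events, they would stay equal or favourable until the evinacumab rate of other serious events reached about 29%, 33% or 37%, for assumed placebo rates of 5%, 10% or 15%.

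These figures rest on assumed non-AP rates and describe the planned trial of 120. They do not predict the final report, where the practical effect is smaller. That AP will be a frequent serious event is inferred from the 30% planning rate and the earlier study; the documents do not rank serious events.

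A reader might go further and want harms judged only on totals without AP. The documents argue against that. AP is a safety question too: three evinacumab and two placebo patients had AP in the earlier double-blind period, and most episodes in the later period came off drug. Both totals are needed. The change should be made, and it concerns reporting only.

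**What to change.** Keep all planned tables. In SAP 5.8.1 and protocol 11.4.5.1, add to the TEAE overview, the serious-TEAE summary and the maximum-severity summary a row for patients with at least one event other than AP. Show that row in two versions:

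1. excluding positively adjudicated AP, so that suspected AP judged negative stays in as an ordinary adverse event;
2. excluding all investigator-reported AP.

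The second version is needed because protocol 9.2.2.1 ties the adjudicated measure to the double-blind period, while the TEAE window runs well beyond it, and SAP 5.8.1 allows for events still in adjudication. Together the two versions cover AP after week 52 and AP not yet adjudicated.

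State the between-arm conclusion on harms from the all-event and AP-excluded totals side by side. No version for discontinuations is needed.

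The cost is a little SAP and protocol wording and a few table rows, built from adverse-event terms and adjudication outcomes that the plan already uses. The drawback is that the affected totals appear in more than one version, so the report must label them clearly.
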